#### **14.2.7      *Protocol Deviations***

Unless there is a safety concern, there should be no deviations from the study protocol. In the event of a safety concern, the investigator or designee must document and explain the reason for any deviation from the approved protocol. The investigator may implement a deviation from, or a change to, the protocol to eliminate an immediate hazard to participants without prior EC approval. Immediately after the implemented deviation or change, the investigator must submit a report explaining the reasons for the protocol deviation to the EC and MyoKardia, if required. The medical monitor will notify the study monitor of the decision.

#### **14.2.8      *Blood Sample Collection/Storage***

Blood samples that are collected as part of routine medical care or as part of protocol procedures may be stored and analyzed for PK or PD analyses.

After the study, samples may be used for additional investigation to help identify factors that may influence response to therapy. Such samples will be used in compliance with guidelines defined by [US FDA Guidance on Informed Consent for \*In Vitro\* Diagnostic Device Studies Using Leftover Human Specimens That Are Not Individually Identifiable](#) (issued

25Apr2006) and European Medicines Agency's [Reflection Paper on Pharmacogenomic Samples, Testing and Data Handling](#).

#### **14.3 Clinical Trial Insurance**

Clinical trial insurance has been undertaken according to the laws of the countries where the study will be conducted. An insurance certificate will be made available to the participating clinical sites upon request.

#### **14.4 Protocol Amendments and Study Administrative Letters**

Study procedures will not be changed without the mutual agreement of the investigator and MyoKardia.

If there are any substantial changes to the study protocol, then these changes will be documented in a study protocol amendment and, where required, in a new version of the study protocol.

The amendment should be approved by the EC and the appropriate regulatory authority(ies), before implementation, as appropriate. Local requirements should be followed for revised protocols.

If a protocol amendment requires a change to the ICF, the EC will need to approve the revised ICF before the revised form is used.

If there are nonsubstantial changes such as clarification of statement or corrections to obvious errors/typos/inconsistencies in the protocol, or change to logistical or administrative aspects, then MyoKardia may issue an Administrative Letter. If local regulations require any administrative change, it will be communicated to or approved by the EC.

**15 DATA QUALITY ASSURANCE**

Quality assurance and quality control systems will be implemented and maintained per Standard Operating Procedures by MyoKardia, as appropriate, to ensure that this clinical study is conducted and data are generated, documented (recorded), and reported in compliance with the protocol, [ICH E6 GCP: consolidated guidance](#) and the applicable regulatory requirements.

## **16 ADMINISTRATIVE CONSIDERATIONS**

### **16.1 Use of Computerized Systems**

This study will require the use of the following electronic data collection methods:

- EDC system to capture protocol-required participant data: clinical sites will enter data from source documents onto eCRFs for each study visit using a web-based interface. Study monitors and data management personnel will use this system to review data and generate queries and reports as needed
- Cardiac clinical data management systems will be used to analyze ECG, CPET, and echocardiographic data from digital equipment used by clinical site personnel to collect participant data
- IXRS to dispense IMP and transfer data in double-blind manner
- Electronic clinical outcomes assessment equipment to allow participants to complete questionnaires

In addition, other central data management systems/databases and software may be used to collect and analyze study data:

- Laboratory Information Systems or proprietary systems will be used by laboratories for storing and/or analyzing bioanalytical laboratory data collected throughout the study
- Statistical software will be used for the statistical analysis of the study data as outlined in the SAP

Information on the above systems will be provided to the investigator, clinical site personnel, and other personnel as appropriate. Measures will be taken to ensure data security and accuracy, including but not limited to user training, granting of user accounts and privileges to trained and authorized personnel in a role-based manner, username/password/electronic signature requirements enforcement, programmed and manual edit checks as outlined in data validation specifications, computer generated audit trails, centralized data management, and routine study monitoring. The systems used will be compliant with US 21 CFR Part 11 and Annex 11 to the Rule Governing Medicinal Products in the European Union and the data collected will be archived (at minimum) for the period specified by applicable regulatory requirements.

### **16.2 Study Records**

The investigator and affiliated institution shall maintain the study documents and records as specified in “Essential Documents for the Conduct of a Clinical Trial” (ICH E6 Section 8), and as required by the applicable regulatory requirement(s). This includes, but is not limited

to, the protocol, eCRFs, AE reports, participant source data (original records or certified copies), correspondence with health authorities and EC, consent forms, investigator's curriculum vitae, monitor visit logs, laboratory reference ranges and laboratory certification or quality control procedures, and laboratory director curriculum vitae.

The eCRF must be completed at the time of, or shortly after the participant's visit or upon receipt of test results. Information will be provided to clinical site staff on the proper way to complete the eCRF.

A copy of each participant's eCRF will be maintained by the investigator.

**17 PUBLICATION**

The data and results of the study will be owned solely by MyoKardia and shall be confidential information of MyoKardia, participant to the investigator's publication rights, all as outlined in the agreement between the investigator/institution and MyoKardia regarding the conduct of the clinical study (the "Clinical Study Agreement"). It is understood by the investigator that MyoKardia may use the information developed in this study in connection with the development of MyoKardia's proprietary IMP and, therefore, may disclose such information as necessary or useful to other clinical investigators or regulatory agencies. To allow for the use of the information derived from the study, the investigator understands that he/she has an obligation to provide and disclose all study results and all data developed during this study to MyoKardia.

Any publication or presentation of the results or data of this clinical study by the investigator may only be made in strict compliance with the provision of the Clinical Study Agreement. The investigator understands that it is not MyoKardia's intention to prevent publication of the data generated in the study; rather, MyoKardia reserves the right to control the form and timing of such publication for commercial reasons and desires to confirm the scientific accuracy of such information prior to such publication or presentation.

[REDACTED]

[REDACTED]

[REDACTED]

[REDACTED]

[REDACTED]

[REDACTED]

**APPENDIX 1        LABORATORY ASSESSMENTS**

The following safety laboratory parameters will be measured by the central laboratory:

Hematology/Coagulation	Serum Chemistry	Urinalysis a

 
• CBC, including differential count
 
• Platelet count
 
• INR
 
• aPTT
 
	
 
• Sodium
 
• Potassium
 
• Chloride
 
• Bicarbonate
 
• Calcium
 
• Magnesium
 
• BUN
 
• Creatinine
 
• ALP
 
• ALT
 
• AST
 
• Total bilirubin
 
• CPKb
 
• Glucose
 
• Protein
 
• Albumin
 
	
 
• Specific gravity
 
• pH
 
• Protein
 
• Glucose
 
• Leukocyte esterase
 
• Blood
 

ALT, alanine aminotransferase; ALP, alkaline phosphatase; aPTT, activated partial thromboplastin time; AST, aspartate aminotransferase; BUN, blood urea nitrogen; CBC, complete blood count; CPK, creatine phosphokinase; INR, international normalized ratio.

a Urine microscopy will be performed if there is a significant abnormality in the dipstick.

b If CPK is high, troponin I will be performed and reported.

At the investigator's discretion, safety laboratory assessments may be repeated on Day -1 to confirm study eligibility before dosing of study medication.

The following nonsafety laboratory parameters will be measured at Screening:

- Hepatitis panel (hepatitis B virus and hepatitis C virus)
- Human immunodeficiency virus test
- Follicle-stimulating hormone
- Thyroid-stimulating hormone

## APPENDIX 3      POTENTIAL DRUG-INDUCED LIVER INJURY REPORTING AND ADDITIONAL ASSESSMENTS REPORTING

To facilitate appropriate monitoring for signals of drug-induced liver injury (DILI), cases of concurrent aspartate/alanine aminotransferase (AST/ALT) and total bilirubin (TBL) elevation according to the criteria specified in [Section 7.4](#) ( $3 \times$  upper limit of normal [ULN] for AST/ALT and  $2 \times$  ULN for TBL in participants with no underlying liver disease and eligibility criteria requiring normal liver function at baseline) require the following:

- The event is to be reported to MyoKardia as a serious adverse event (SAE) within 24 hours of discovery or notification of the event (ie, before additional etiologic investigations have been concluded).
- The appropriate eCRF (eg, Adverse Event eCRF) that captures information necessary to facilitate the evaluation of treatment-emergent liver abnormalities are to be completed and sent to MyoKardia.

Other events of hepatotoxicity and potential DILI are to be reported as SAEs if they meet the criteria for an SAE defined in [Section 11.1.2](#).

### Additional Clinical Assessments and Observation

All participants for whom investigational product(s) or protocol-required therapies is/are withheld (either permanently or conditionally) due to potential DILI or who experience AST/ALT elevations  $> 3 \times$  ULN are to undergo a period of “close observation” until abnormalities return to normal or to the participant’s baseline levels. Assessments that are to be performed during this period include the following:

- Repeat liver chemistries within 24-48 hours (ALT, AST, alkaline phosphatase [ALP], TBL); in cases of TBL  $> 2 \times$  ULN or AST/ALT much greater than  $3 \times$  ULN, retesting is to be performed within 24 hours.
  - For participants that are far away from the trial site, it may be difficult for the participants to return to the trial site promptly. In this case, the participants should be retested locally, but normal laboratory ranges should be recorded, results should be made available to trial investigators immediately, and the data should be included in the case reports.
  - Participants are to be monitored at least twice weekly; testing frequency may decrease to once per week or less if laboratory abnormalities stabilize or the investigational product(s) or protocol-required therapies have been discontinued AND the participant is asymptomatic.
- Obtain prothrombin time/international normalized ratio, fractionated bilirubin, and any other potentially relevant laboratory evaluations of liver function or disease.
- Obtain complete blood count with differential to assess for eosinophilia.

- Obtain appropriate blood sampling for pharmacokinetic (PK) analysis if it has not already been collected.
- Obtain a more detailed history of the following:
  - Prior and/or concurrent diseases or illness
  - Exposure to environmental and/or industrial chemical agents
  - Symptoms (if applicable) including right upper quadrant pain, hypersensitivity-type reactions, fatigue, nausea, vomiting, and fever
  - Prior and/or concurrent use of alcohol, recreational drugs, and special diets
  - Concomitant medications (including nonprescription medicines and herbal and dietary supplements)
- Initiate full viral and autoimmune hepatitis evaluation (serologies for hepatitis A, B, C, D, E, Epstein-Barr virus, herpes simplex virus, etc.); evaluate for other potential causes of DILI, including but not limited to non-alcoholic steatohepatitis, hypoxic/ischemic hepatopathy, and biliary tract disease.
- Obtain gastroenterology or hepatology consult.
- Perform appropriate liver imaging or biopsy if clinically indicated; strongly consider these tests in cases of concurrent transaminase and TBL elevation as specified in [Section 7.4](#).
- Follow the participant until all laboratory abnormalities return to baseline or normal. The “close observation period” is to continue for a minimum of 4 weeks after investigational product(s) or protocol-required therapies discontinuation.

The potential DILI event and additional information such as medical history, concomitant medications and laboratory results must be captured in corresponding eCRFs.

SD	standard deviation
SOC	system organ class
SRT	septal reduction therapy
SUSAR	suspected unexpected serious adverse reactions

TBL	total bilirubin
TEAE	treatment-emergent adverse event
TSH	thyroid-stimulating hormone
TTE	transthoracic echocardiography, transthoracic echocardiogram
ULN	upper limit of normal
US	United States
VCO ₂	carbon dioxide production
VE	volume expired
VO ₂	oxygen uptake

The image consists of a large, solid black rectangular area. On the right side, there is a prominent, jagged white edge that tapers to a point. This white edge is composed of several thick, horizontal white lines of varying lengths. The entire image is surrounded by a thick black border. In the top left corner, there is a small, solid black rectangular element. The overall appearance is that of a high-contrast, binary image, possibly a scan of a physical object or a specific type of digital artwork.

2. STUDY OBJECTIVES

2.1. Primary Objective

The primary objective of this study is to evaluate the safety and tolerability of a 16-week course of mavacamten in individuals with symptomatic nHCM.

[figure not shown]
3. OVERALL STUDY DESIGN AND PLAN

This is a Phase 2, multicenter, exploratory, randomized, double-blind study to evaluate the safety, tolerability, preliminary efficacy, PD, and PK of 2 target drug concentrations of mavacamten compared with placebo in patients with symptomatic nHCM.

Approximately 60 patients with symptomatic nHCM will be enrolled. Patients will be randomized in a 1:1:1 ratio to receive a 16-week course of mavacamten doses titrated to achieve 1 of 2 target drug concentrations (Group 1: ~200 ng/mL; Group 2: ~500 ng/mL) or placebo once daily (QD). Randomization will be stratified according to current treatment with beta blocker (yes or no) and type of exercise testing (treadmill or bicycle). Patients will be treated for 16 weeks and then followed up approximately 8 weeks after the last dose of study drug. At Week 6, all patients will undergo blinded dose adjustment based on Week 4 assessments. Patients who are treated for their HCM condition (eg, beta blocker or calcium channel blocker) should receive a stable dose of such treatment for at least 2 weeks prior to Screening, and every effort should be made to keep such treatment unchanged (ie, at the same dose) throughout the entire study duration until the EOS visit at Week 24.

During the Screening process, patients will undergo a variety of general, cardiopulmonary, laboratory, exploratory biomarker, patient-reported outcomes (PRO), and symptom assessments. Patients will receive their first dose of study drug on Day 1. Patients will then undergo a variety of assessments every 2 weeks through Week 16. Assessments will be conducted at the clinical site at Weeks 4, 6, 8, 12, and 16; assessments will be conducted via telephone call at Weeks 2, 10, and 14. At Week 24, patients will undergo EOS procedures.

PRO questionnaires will be completed either on paper or on an electronic device provided to each patient during the Screening period or on an app installed on the patient's own electronic device.

3.1. Study Duration

The expected study duration is approximately 28 weeks: up to 4 weeks for Screening and 16 weeks (\pm 7 days) for study conduct, and 8-week posttreatment follow-up period.

3.2. Independent Data Monitoring Committee

An Independent Data Monitoring Committee (IDMC) will meet at regular intervals to review study data. The role of the IDMC will be to act in an advisory capacity to the Sponsor with respect to safeguarding the interest of study patients, assessing interim safety data, and advising the Sponsor and investigators on important emerging study conduct issues. The IDMC may formulate recommendations in relation to the evaluation procedures and methodologies being employed to survey and detect potential safety signals. Meeting frequency and membership is described in the IDMC Charter.

3.3. Treatment Withholding and Discontinuation

Patients with abnormal hepatic laboratory values (eg, alkaline phosphatase [ALP], aspartate aminotransferase [AST], alanine aminotransferase [ALT], total bilirubin [TBL], or international normalized ratio) or signs/symptoms of hepatitis may meet the criteria for withholding of study medication or other protocol-required therapies. Withholding is either permanent or conditional depending on the clinical circumstances discussed in the protocol.

Patients with exaggerated pharmacologic effect (systolic dysfunction), higher than expected plasma concentration, or excessive QT prolongation, may discontinue study treatment as described in the protocol

4. RANDOMIZATION AND BLINDING PROCEDURES

4.1. Randomization

Patients who meet the inclusion/exclusion criteria will be randomized via an IXRS to 1 of 3 groups in a 1:1:1 ratio: 2 active treatment groups and 1 matching placebo group. Randomization will be stratified according to current treatment with beta blocker (yes or no) and type of exercise testing (treadmill or bicycle).

4.2. Study Blinding

Patients will be randomized to 1 of 3 groups via the IXRS. All patients receive either 5 mg mavacamten or matching placebo daily from Day 1 to Week 6. Blinded dose adjustment (to 2.5,

5, 10, or 15 mg mavacamten or placebo daily) via the IXRS will begin at Week 6 based on PK measurements at Week 4. Study drug administration will occur in a double-blind manner via the IXRS such that the investigator, site staff, the pharmacist, and the patient will not know which study drug is being administered.

In addition, the Sponsor, the central and core laboratories, and clinical site monitors will be blinded to assigned treatment. Echocardiography results (eg, LVEF) performed at clinic visits will be blinded to the investigator and study staff. The 4 different doses of mavacamten and matching placebo will be identical in appearance in order to preserve the blind. Study drug (2.5, 5, 10, or 15 mg mavacamten or matching placebo) will be labeled with a unique identifying number that will be assigned to a patient through the IXRS.

Members of the pharmacovigilance team will be unblinded for suspected unexpected serious adverse reaction (SUSAR) reporting. The IDMC may also review unblinded safety and efficacy data.

4.3. Methods for Unblinding

Unblinding by the investigator independently of the Sponsor also may occur if an AE or toxicity necessitates identification of the medication for the welfare of the patient. Please refer to the IXRS Manual for the unblinding process.

5. DETERMINATION OF SAMPLE SIZE

This study will include a total of approximately 60 patients, or approximately 20 patients per treatment group. Such a sample size will be sufficient to obtain sound variability estimates while yielding reasonable effect size estimates for future planning purposes.

6. GENERAL STATISTICAL CONSIDERATIONS

The primary analysis will be conducted through the 16-week treatment period. Data collected through this timepoint will be cleaned and locked prior to analysis.

Once all subjects have completed their Week 24/EOS visit, all data will be cleaned and locked, and analyses using this data will be used to inform study objectives relating to follow-up safety and reversibility of drug effect.

SAS® version 9.4 or higher will be used for statistical analyses, tabulations and graphical presentations.

In general, descriptive summaries will be presented by treatment group [placebo, Group 1, Group 2, and overall active]. Summaries of continuous variables will utilize the number of subjects (N), mean, standard deviation (SD), median, minimum and maximum. Descriptive summaries for categorical variables will utilize counts and percentages. Unless otherwise stated, denominators for percentages will be the number of patients in the analysis population with non-missing variable of interest for the column of interest.

The between-group comparisons focus on the comparative performance of Group 1 (target concentration of ~200 ng/mL) vs placebo and Group 2 (target concentration of ~500 ng/mL) vs

placebo. An overall active vs placebo comparison will also be conducted where appropriate. Any statistical test will be conducted at a two-sided significance level of 0.05 using the exact method unless otherwise stated.

In general, baseline is defined as the last non-missing result on or before the first dose date, and time where applicable. For certain data types (e.g., accelerometer, PROs, cardiac rhythm monitoring, etc.), special considerations may be required; please refer to the specific data section for details. Unless otherwise noted, non-safety (ie. efficacy, PD) information displayed “by visit” will utilize analysis visits as defined by the analysis visit window as opposed to the visits at which the information was collected (ie. nominal visit). Data collected at unscheduled or early termination visits will also be mapped to analysis visits. The analysis day for purposes of the visit windows are derived as follows (reference date is the study drug initiation date for the safety population or the randomization date for the ITT population):

- If date of information is missing, analysis day cannot be calculated and leave as missing
- If date of information < reference date, analysis day = analysis date – reference date.
If date of information \geq reference date, analysis day = (analysis date – reference date) + 1

Safety information will be summarized by the nominal visit (per protocol), and unscheduled visits will be presented in listings only.

The visit windows for efficacy and PD assessments will be as follows, unless otherwise noted in the specific data sections below:

Table 1: Analysis Windows

Analysis Visit	Analysis Visit Window	Analysis Visit Target Day
Day 1 (Baseline*)	Screening \leq analysis day \leq 1	1
Week 4	15 < analysis day \leq 42	28
Week 8	43 \leq analysis day \leq 70	56
Week 12	71 \leq analysis day \leq 98	84
Week 16	99 \leq analysis day \leq 126	112
Week 24	155 \leq analysis day \leq 182	168

Note: CPET only collected on Day 1 and Week 16.

* Per the baseline definition in this section.

When more than one result is available within the same analysis visit, the result collected closest to the target visit day will be used for analysis. If two values tie as closest to the time point (for example, one value is before and the other value is after the target day), then the latest value will be selected as the analysis value. If for a specific analysis window, the last collected time point has 2 or more values collected, for continuous and ordinal (scale) data, the average among these results will be derived. If the data are categorical (eg, Yes/No) then the clinically ‘worse’ measurement will be affiliated with the visit of interest.

[figure not shown]
If a measurement does not fall into an analysis window it will not be included in efficacy summary. However, these measurements will be included in data listings and SAS data sets.

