- TEAE experienced during the pregnancy by primary SOC and PT showing the number and percent of subjects

Overdose

If overdoses occur, the following overdose information will be provided in a by-subject data listing:

- Number of subjects who experienced overdose summarized by treatment received
- Analysis of the cause and occurrence of the overdose
- TEAE, if any, experienced during the overdose by primary SOC, high-level group term, high-level term, and PT showing the number and percent of subjects

13.2. 12-lead Electrocardiogram

The RR, PR, QRS, and QT intervals will be measured and read by a central laboratory. HR will be calculated as $60/(RR \times 1000)$ (with RR expressed in msec) and rounded to the nearest integer.

Correction for Heart Rate

Corrected QT interval (QTc) will be calculated using the manually over-read QT values. Each individual ECG QT value will be corrected for HR. The measured QT data will be corrected for HR using QTcF as per the following formulae/method (with QT, RR and QTc expressed in msec):

Fridericia's Correction:

$$QTcF = \frac{QT}{(RR/1000)^{(1/3)}}$$

ECG Numeric Variables

HR, PR, QRS, and QTcF will be summarized using descriptive statistics. The change from baseline of these ECG parameters at each time point will be listed for each patient. For each time point of measurement, the changes from baseline will be summarized using descriptive statistics.

Categorical Analysis

The incidence count and percentage of subjects with any postdose QTcF values of > 450 msec, > 480 msec, and > 500 msec will be tabulated for all subjects. Subjects with QTc values > 500 msec will be listed with corresponding baseline values, Δ QTcF, and baseline and treatment HR. The incidence count and percentage of subjects with Δ QTcF increase from baseline of > 30 msec and > 60 msec will be tabulated.

Morphology Findings

ECG morphologies for each patient will be listed.

Concentration-QTc Analyses

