13.3. Safety Laboratory Data

The summary statistics (including number, mean, median, SD, minimum and maximum) of all safety laboratory tests (ie. hematology and chemistry panels) will be calculated for each visit (baseline and post-baseline time points) and presented by treatment group.

Shift tables reflecting changes from baseline (i.e., normal to low, high, etc.) will be presented in lieu of descriptive statistics of changes from baseline. Listings of subjects with laboratory values that are out of the reference range will be produced.

Potential drug-induced liver injury

The liver function tests, namely ALT, AST, ALP (alkaline phosphatase), and TBL (total bilirubin), will be used to assess possible drug-induced liver toxicity.

A graph of distribution of peak values of ALT versus peak values of TBL will be presented. Note that the ALT and TBL values are presented on a logarithmic scale. The graph will be divided into 4 quadrants with a vertical line corresponding to $3 \times$ ULN for ALT and a horizontal line corresponding to $2 \times$ ULN for TBL.

The number of subjects with elevated liver function tests will be summarized in a table by categories of elevation ($3 \times$ ULN, $5 \times$ ULN, $10 \times$ ULN, $20 \times$ ULN for ALT and AST, $1.5 \times$ ULN for ALP, and $1.5 \times$ ULN and $2 \times$ ULN for TBL), along with the following categories of normalization (to $\leq 1 \times$ ULN or return to baseline if baseline $>$ ULN): never normalized,

normalized after permanent discontinuation of study drug. Note that a patient will be counted only under the maximum elevation category (1-3 \times ULN, 3-5 \times ULN, 5-10 \times ULN, 10-20 \times ULN, $>$ 20 \times ULN).

If identified, the number of subjects with concurrent ALT/AST of 3 \times ULN or higher, TBL of 2 \times ULN or higher, and ALP below 2 \times ULN (possible Hy's Law cases) will also be summarized in this table and included in a by-subject listing as well.

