13.6. Other Safety Analyses

Abnormal physical examination results will be listed by subject, and clinical significance. Medical history, concomitant, and prior medications will be summarized in tables and listings.

HCM history, including frequency of SRT (septal reduction therapy) will be summarized in a separate table by treatment and overall.

The number of subjects who met each IMP stopping criteria per protocol will be summarized by treatment and overall.

[REDACTED]

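### The SAP's listings-only rule for unscheduled safety visits is not limited to by-visit tables, and the visible text does not reconcile it with the worst-value liver and QTcF outputs

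*SAP*

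**What the plan says.** SAP 6 has two rules for assigning data to visits. The non-safety rule reads "Unless otherwise noted, non-safety (ie. efficacy, PD) information displayed “by visit” will utilize analysis visits", and continues: "Data collected at unscheduled or early termination visits will also be mapped to analysis visits". The safety rule follows shortly after: "Safety information will be summarized by the nominal visit (per protocol), and unscheduled visits will be presented in listings only".

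SAP 13.2 and 13.3 then define safety outputs with no nominal visit attached:

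- **QTcF:** subjects with "any postdose QTcF values of > 450 msec, > 480 msec, and > 500 msec will be tabulated for all subjects", plus increases from baseline above 30 and 60 msec.
- **Liver plot:** "A graph of distribution of peak values of ALT versus peak values of TBL will be presented".
- **Liver table:** "a patient will be counted only under the maximum elevation category", with normalization status alongside.
- **Possible Hy's Law:** concurrent ALT/AST, TBL and ALP criteria, where the number of subjects "will also be summarized in this table and included in a by-subject listing as well".

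The common rules at the head of SAP 13 cover baseline, descriptive analysis and a safety period running to 56 days past the last dose. They do not mention unscheduled data.

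The protocol expects such data. Section 9.3.3 has extra safety ECGs recorded as unscheduled. Section 9.5 puts data from unscheduled visits in the clinical database. Appendix 3 calls for liver retests within 24-48 hours of a signal and then at least twice weekly, with less frequent testing allowed later.

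**The concern.** Values taken because something looks abnormal are the ones most likely to hold a participant's maximum, and the safety rule as written sends them to listings only. The non-safety rule carries an exception clause and a limit to by-visit displays; the safety rule has neither. Two programmers working from this SAP could therefore build different liver tables, peak plots and QTcF categories, each with textual support.

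Safety and tolerability are the primary objective (SAP 2.1), and the frequency of laboratory abnormalities is a listed endpoint (SAP 6.1). If the literal reading were programmed, high categories could be understated, lower ones overstated, and a recovery seen only on a retest would not be counted.

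**Working it through.** The plan states no figure on this point, so there is none to reproduce. The check compares the text and then traces cases through it.

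**1. Scheduled values.** The schedule in SAP Appendix A puts chemistry and ECG after the first dose at Weeks 4, 8, 12, 16/ET and 24, on target days 28, 56, 84, 112 and 168. The gaps are 28, 28, 28 and 56 days. A retest 24-48 hours after one of these visits has no scheduled slot of its own.

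**2. Case on study drug (assumed values).** Week 8 ALT is 3.5 × ULN with normal TBL. Retests show ALT between 5 and 8 × ULN for less than 2 weeks, without symptoms, with monitoring kept up and TBL still normal. Neither Protocol 7.4.1 nor 7.4.2 then requires stopping or withholding, so no ET visit follows from those criteria. If ALT is lower by Week 12, then in a group of 20:

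| Row | Literal reading | All values |
|---|---|---|
| 3-5 × ULN | 1/20 | 0/20 |
| 5-10 × ULN | 0/20 | 1/20 |

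**3. Case with raised bilirubin (assumed values).** Week 8 is as above, but the retest shows ALT 9 × ULN, TBL 2.5 × ULN and ALP below 2 × ULN.

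- If the remaining 7.4.1 conditions hold (baseline below ULN, no other apparent cause), drug is stopped permanently. Protocol 10.1.4 asks for a prompt ET visit with Week 16 procedures. Its chemistry may capture the case, so a zero count does not necessarily follow.
- If another cause is apparent, 7.4.1 is not met, and the ET request arises only if the stop becomes permanent. SAP 13.3 sets no cause condition for possible Hy's Law. If no scheduled value still qualifies, the literal count is 0/20 instead of 1/20.

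**4. Size of one participant.** 1/20 = 5 percentage points; for overall active, about 1/40 = 2.5 points. Exact 95% intervals:

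- 0/20: upper limit 1 − 0.025^(1/20) = 16.8%, so 0 to 16.8%.
- 1/20: lower limit 1 − 0.975^(1/20) = 0.1%. The upper limit solves (1−p)^20 + 20p(1−p)^19 = 0.025, giving 24.9%.

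These show the effect of one misplaced participant, not how likely it is.

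**5. How often a short episode meets a scheduled visit (illustration).** Assume onset is uniform over whole days and ignore ET visits. Share = onset days for which a scheduled visit falls within the episode ÷ possible onset days.

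| Episode length (days) | Onset days 2-112 | Onset days 2-168 |
|---|---|---|
| 3 | 12/111 = 11% | 15/167 = 9% |
| 7 | 28/111 = 25% | 35/167 = 21% |
| 14 | 56/111 = 50% | 70/167 = 42% |
| 21 | 84/111 = 76% | 105/167 = 63% |
| 28 | 111/111 = 100% | 139/167 = 83% |

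Short episodes can fall between visits. The table does not say how often they occur or how often an unscheduled sample would catch them.

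**6. Normalization rows (separate from the visit rule).** SAP 13.3 has two categories: never normalized, and normalized once drug has been permanently stopped. A participant who normalizes on drug, or after the conditional withholding of Protocol 7.4.2, fits neither.

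**The case against.** The strongest reply is that the literal reading cannot be what was meant. Adverse events, deaths and stopping criteria are safety information too, and SAP 13.1 and 13.6 summarize none of them by visit. The sentence sits among the analysis-day and visit-window rules, where the question is which visit label to use. Wording such as any postdose, peak and maximum sets its own scope within a safety period defined by time, and a specific rule normally prevails over a general one. This stands: a by-visit-only intent is likely. It is still an inference, because no visible sentence says so. The content of SAP 16 is not shown.

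A reader might go further and infer that the plan will discard unscheduled values, that only five fixed visits can set a maximum, or that a Hy's Law case would be hidden. The documents do not support these readings. Besides the likely intent, ET shares a scheduled column with chemistry and ECG. Appendix 3 has concurrent transaminase and bilirubin elevations reported as SAEs, which would reach the SAE tables. SAP 13.6 adds "The number of subjects who met each IMP stopping criteria per protocol will be summarized by treatment and overall", and listings keep every value.

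These safeguards do not correct the outputs themselves. The QTcF stopping threshold in Protocol 7.5 is 500 ms or more, so the 450 and 480 msec categories and both change categories have no counterpart there. Protocol 7.4.1 carries baseline and cause conditions that the SAP's Hy's Law count lacks.

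It is also fair that an unscheduled assessment can take place at a scheduled visit, and that Appendix 3 retests are required by protocol rather than discretionary. Whether the SAP's term covers them is itself unsettled, which is a further reason to define it.

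**Conclusion.** The point holds as an unresolved conflict in the visible text, with medium confidence; it is worth settling before database lock. It does not show that values will be lost. The exposure is mainly a peak, threshold crossing or recovery seen only between scheduled or ET visits, especially in participants who stay on drug or have it withheld temporarily. How many would be affected cannot be estimated from the documents.

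This rests on two assumptions: that the SAP's unscheduled visits include retests and extra ECGs with no nominal visit, and that no unseen text settles the matter. The gap in the normalization categories is a smaller point and depends on neither.

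**What to change.** - **SAP 6:** limit the nominal-visit and listings-only rule to by-visit descriptive tables.
- **SAP 13.2 and 13.3:** state that worst-value, threshold, possible Hy's Law and normalization outputs use all post-first-dose values in the treatment-emergent period, whether scheduled, ET or unscheduled. Include local retests as multiples of the local ULN where the range is recorded.
- **Separately, SAP 13.3:** add rows for normalized on study drug and normalized after temporary withholding.

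The cost is a sentence or two, a programming filter and two table rows. No new data are needed: Protocol 9.5 already captures discretionary unscheduled visits, and Appendix 3 already requires local results with their ranges and entry of liver-injury laboratory results in the eCRF. The downside is slightly higher counts in the upper categories and some ULN scaling, since Appendix 1 otherwise assigns safety laboratory tests to the central laboratory.
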